2.2.2.2. Clinical Pharmacokinetics

The clinical PK of PF-06882961 in healthy adult participants has been evaluated in three completed studies: C3421001, C3421002, and C3421003. The results of these completed studies are summarized in the PF-06882961 IB.

The PK properties of PF-06882961 have been evaluated in adult participants with T2DM as part of the completed C3421002 study. In this study, the first 6 cohorts received PF-06882961 or placebo dosed BID. Four of the 6 cohorts were titrated for various amounts of time over the 28 days, with a target maximum dose ranging between 10 and 120 mg BID across the 6 cohorts. Approximately dose proportional increases in C_{max} and AUC_{24} were observed between the doses of 10 mg BID and 120 mg BID, with C_{max} ranging from 38.38 to 685.2 ng/mL and AUC_{24} ranging from 455.9 to 8368 ng•h/mL. Percent coefficients of variance (%CV) ranged from 32 to 94 and 41 to 87 for C_{max} and AUC_{24} respectively on Day 28. Consistent with data from the completed studies, PF-06882961 was observed to have a $t_{1/2}$ of approximately 4.681 to 8.090 hours. T_{max} ranged from 3 to 6 hours after the AM dose over the dose ranges administered.

2.3. Benefit/Risk Assessment

More detailed information about the known and expected benefits and risks and reasonably expected AEs of PF-06882961 may be found in the IB, which is the SRSD for this study.

2.3.1. Risk Assessment

Potential Risk of Clinical Significance	Summary of Data/Rationale for Risk	Mitigation Strategy
Study Intervention(s) PF-06882961		
Thyroid C-cell tumors	
The potential risks are based on product labeling for injectable GLP-1R agonists (ie, liraglutide, dulaglutide, and exenatide) due to dose-dependent and treatment duration-dependent thyroid C-cell tumors in nonclinical studies in rats and mice at clinically relevant exposures.
 
Thyroid C-cell tumors have not been observed with PF-06882961 in clinical or nonclinical studies.
	Potential participants with a personal or family history of medullary thyroid carcinoma or MEN2 are excluded from the clinical development program. Thyroid function tests are included in the clinical trial protocols to monitor participants' thyroid function.
Pancreatitis	
The potential risks are based on product labeling for injectable GLP-1R agonists (ie, liraglutide, exenatide and dulaglutide).
 
Pancreatitis has not been observed in the PF-06882961 clinical trial program.
	Per exclusion criteria, potential participants with acute pancreatitis or a history of pancreatitis are not eligible for study entry. Serum amylase and lipase are monitored during the clinical studies.
Hypoglycemia	
Clinical trials with injectable GLP-1R agonists have not demonstrated an increased risk for hypoglycemia. However, when administered in combination with anti-diabetic agents that are known to have an increased risk of hypoglycemia (such as insulin or sulfonylureas), an increased risk for hypoglycemia was observed.
 
Only one adverse event of mild hypoglycemia has been reported in the clinical development program to date.
	Blood glucose is monitored frequently during clinical studies involving patients with T2DM, and hypoglycemia is a well recognized risk in T2DM patients. The IB and ICD inform of the potential increased risk of hypoglycemia when PF-06882961 is administered in combination with anti-diabetic agents that are known to have an increased risk of hypoglycemia (such as insulin or sulfonylureas), which are prohibited in this study.
Impairment in renal function	In rats, minimal renal tubular vacuolation was observed, but this finding was considered to be non-adverse.	Per exclusion criteria, potential participants with significant renal impairment (<60 mL/min/1.73 m ²) are not eligible for study entry. Renal function is monitored at each study

PFIZER CONFIDENTIAL

	
In the clinical trial program only one mild AE (Blood creatinine increased) has been observed in the clinical trial program.
	visit by the central lab assessments of serum BUN, creatinine and eGFR.
Gastrointestinal adverse reactions	
The potential risks are based on product labeling for injectable GLP-1R agonists (ie, liraglutide, exenatide and dulaglutide). In addition, gastrointestinal AEs, the majority of which were mild in severity, have been observed in the clinical program with PF-06882961. In nonclinical studies with PF-06882961, gastrointestinal adverse effects have been seen in rats and monkeys.
	Participants are monitored during the clinical study visits, via body weight, vitals signs and laboratory assessments, to prevent potential sequelae of any severe gastrointestinal reactions, eg, dehydration.
Diabetic retinopathy complications	
The potential risk is based on the product labeling for the injectable GLP-1R agonist semaglutide for T2DM. This risk has not been listed in the prescribing information for other marketed GLP-1R agonists.
 
There are no nonclinical or clinical data involving PF-06882961 to suggest an increased risk of diabetic retinopathy complications.
	Potential participants with a known medical history of active proliferative retinopathy and/or macular edema are excluded from the clinical studies.
Study Procedures		
Use of a placebo arm	Participants randomized to placebo may not experience glycemic lowering effect.	A majority of the randomized study population will receive PF-06882961, and all participants will receive lifestyle counseling, which is standard of care for management of T2DM. And, all participants will be monitored for significant hyperglycemia.

2.3.2. Benefit Assessment

[figure not shown]
Based on the clinical experience of injectable GLP-1R agonists, a GLP-1R agonist is expected to improve glucose control, reduce HbA1c levels, diminish food intake, and decrease body weight in patients with T2DM. A treatment period of 8 weeks of PF-06882961 in this study has limited clinical benefit to participants with T2DM. This study is designed to generate safety, tolerability, PK CCI data in Japanese T2DM participants for further clinical development.

2.3.3. Overall Benefit/Risk Conclusion

Considering all available clinical and nonclinical data, the benefit-risk profile of PF-06882961 supports continued clinical development in patients with T2DM.

3. OBJECTIVES AND ENDPOINTS

Objectives	Endpoints
Primary:	Primary:

 • To evaluate the safety and tolerability of multiple, oral doses of PF-06882961, administered to adult Japanese participants with T2DM. 	
 • Incidence of treatment emergent AEs (AEs and SAEs), clinical laboratory abnormalities, vital signs and ECG parameters during the entire study.
Secondary:	Secondary:

 • To characterize plasma pharmacokinetics of PF-06882961 following Day 1 and following multiple, oral doses administered to adult Japanese participants with T2DM. 	
 • PF-06882961 plasma pharmacokinetic parameters AUC₂₄, C_{max}, T_{max}, t_{1/2} (as defined in Section 9.4.3.1, as appropriate for the dosing paradigm) following Day 1, and multiple dose administration, as data permit.
CCI	

4. STUDY DESIGN

4.1. Overall Design

This is a Phase 1, randomized, double-blind (sponsor-open), placebo-controlled, 4-arm, parallel group study of PF-06882961 in adult Japanese participants with T2DM inadequately controlled on diet and exercise alone.

Participants will receive oral doses of PF-06882961 or placebo in this study. Approximately 9 participants will be enrolled in each arm, for a total of approximately 36 (4 arms) participants randomized. The randomization ratio will be 1:1:1:1 (1 of 3 active dosing regimens of PF-06882961 or placebo), and all 4 arms will be enrolled in parallel. The study will be conducted at a single clinical site in Japan.

Target dose levels, achieved after completion of titration, for the 4 arms of the study are placebo and PF-06882961 doses of 40 mg BID, 80 mg BID, and 120 mg BID. Dose titration will be incorporated to enhance tolerability to PF-06882961.

The maximum dose of PF-06882961 in this study will not exceed 120 mg BID.

Following the screening period to confirm eligibility (up to 4 weeks), the treatment period will be approximately 8 weeks, followed by an approximate 4-week follow-up. The total duration of participation in this study is approximately 12 weeks, not including the screening period. Dosing will occur with food BID, and up to 2 weeks (The target dose level: 40 mg BID), 4 weeks (The target dose level: 80 mg BID) or 6 weeks (The target dose level: 120 mg BID) of the 8-week dosing duration will be used for dose titration to maximize tolerability of PF-06882961, as depicted in [Figure 1](#) and [Table 3](#). Downward titration or dosing is not permitted during the study; participants who do not tolerate the titration scheme and/or assigned dose may be required to discontinue dosing of study intervention.

This study includes a total of 12 visits, of which 2 are inpatient study visits at the site and 7 are outpatient visits excluding screening to the site. The other visits are Follow-up visit and Follow-up telephone contact. Participants will be randomized at V2 to receive PF-06882961 or matching placebo for a duration of 8 weeks, with completion of dosing at V10. The inpatient stays at V2 and V10 consist of 4 days and 3 nights as listed in the [SOA](#). For the study duration between the inpatient study visits, participants will continue dosing with blinded study intervention provided in blister packs, either at home or at an outpatient visit to the study site.

A Follow-up visit and a Follow-up contact (may be a phone call) will occur on V11 (Day 63-70) and on V12 (Day 84-91) following the first dose of study intervention on Day 1, respectively. Participants who discontinue prior to completion of the study for non-safety related reasons may be replaced, at the discretion of the PI and Sponsor.

The formulation administered in this study will be PF-06882961 tablets, or matching placebo (see [Section 6](#)). A study design overview is shown in [Section 1.2](#) and [Table 3](#).

4.2. Scientific Rationale for Study Design

The purpose of this study is to evaluate the safety, tolerability, and PK of multiple oral doses of PF-06882961 in adult Japanese participants with T2DM who are receiving no background anti-hyperglycemic medication. [CCI](#)

Target dose levels, achieved after completion of titration, for the 4 arms of this study are placebo and PF-06882961 doses of 40 mg BID, 80 mg BID, and 120 mg BID. Dosing titration schemes are shown in [Table 3](#).

A baseline day (Day -1) with time-matched procedures will permit an improved assessment of safety, tolerability, [CCI](#) within participant and placebo-adjusted comparison of dose-response (between participant), as appropriate. The participants and site staff will be blinded to administration of each treatment to permit an unbiased assessment of safety. However, a limited number of members of the Sponsor team will be unblinded to permit review of safety and tolerability while the study is ongoing.

Based on the tolerability data from C3421002, the titration will start at PF-06882961 10 mg BID (or matching placebo), then with increase every week to reach the target dose level of 40 mg BID at the start of Week 3, to reach the target dose level of 80 mg BID at the start of Week 5, and to reach the target dose level of 120 mg BID at the start of Week 7.

All doses will be blinded and consist of 3 tablets administered BID via a blister pack, and dosing regimens will look the same throughout the 8-week dosing duration post randomization.

Clinical safety laboratory tests, assessments of vital signs and 12-lead ECGs, and AE monitoring will provide essential data to evaluate the safety and tolerability of PF-06882961.

In an effort to reduce variability and better quantify potential changes, all measurements of ECG intervals, heart rate and BP will be collected in triplicate (except as noted in the [SOA](#)) and the mean values will be used for analysis at each time point. In addition to triplicate ECG and BP measurements taken prior to dosing of study intervention, triplicate ECG and BP measurements will also be collected at the approximate time to reach C_{max} (T_{max}) on PK sampling days as specified in the [SOA](#) to further enhance quantification of any possible drug effect.

As part of the clinical safety laboratory tests, calcitonin, amylase, and lipase will be assessed, as these laboratory parameters have been shown to increase with marketed GLP-1R agonists.¹² In addition, TSH, FT4, lipid profile, coagulation profile, and TBA will be assessed, based on non-adverse findings in the nonclinical studies with PF-06882961.

GLP-1R agonists typically are not associated with hypoglycemia unless co-administered with anti-diabetic agents that can cause hypoglycemia (such as insulin or sulfonylureas), which are prohibited in this study. Blood glucose concentrations will be monitored throughout the study via glucometer, and monitoring of symptomatic hypoglycemic AEs will be performed. In addition, all participants will be instructed on Day -2 regarding the symptoms associated with, and management of, hypoglycemia, which will permit the monitoring of symptomatic HAEs.

The potential risk of exposure to PF-06882961 in a sexual partner of a male participant in this study via ejaculate is low, and therefore no contraception (condom) use in male participants is warranted. The calculated safety margin is \geq 100-fold between the estimated partner exposure due to seminal transfer and the NOAEL for serious manifestations of developmental toxicity in nonclinical studies. The safety margin of 100-fold is based on applying a 10-fold safety factor for interspecies extrapolation and a 10-fold safety factor for susceptible populations.¹³

Banked Biospecimens will be collected and stored for further analyses which may, for example, provide greater understanding of the study intervention.

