1.3. Schedule of Activities

The SOA tables ([Table 1](#) and [Table 2](#)) provide an overview of the protocol visits and procedures. Refer to the **STUDY ASSESSMENTS AND PROCEDURES** section of the protocol for detailed information on each procedure and assessment required for compliance with the protocol.

The investigator may schedule visits (unplanned visits) in addition to those listed in the SOA table, in order to conduct evaluations or assessments required to protect the well-being of the participant.

Table 1. Overall Schedule of Activities

Protocol Activity (See Appendix 10 for abbreviations)	Screen	Study Day (all activities at 0H [prior to AM meals/dosing] unless otherwise specified)										Follow Up		ET	
Visit	V1	V2		V3	V4	V5	V6	V7	V8	V9	V10		V11	V12 ^a	
Weeks Relative to Dosing on Day 1		0		1	2	3	4	5	6	7	8		9-10	12-13	
Days Relative to Dosing on Day 1 ^b	-28 to -3	Day -2 to Day 1	2	8	15	22	29	36	43	50	Day 55 to Day 56	57	58	63 - 70	84 - 91
Informed consent & demography	x														
Review of eligibility criteria	x														
Discharge from inpatient stay		x										x			
Outpatient visit (after ≥8-H fast)	x		x	x	x	x	x	x	x	x		x			
Adverse event monitoring	x		x	x	x	x	x	x	x	x		x	x	x	x
Medical history	x														
Review prior and concomitant treatments	x		x	x	x	x	x	x	x	x		x	x	x	x
Review drug, alcohol, tobacco use	x		x	x	x	x	x	x	x	x		x	x	x	x
Review contraception use (females only)	x		x	x	x	x	x	x	x	x		x	x	x	x
Review dosing diary, glucometer & glucose log			x	x	x	x	x	x	x	x		x ^c		x	
Glucose measurement (8 hours fasting, via glucometer, on site)			x	x	x	x	x	x	x	x		x			
Physical examination (height at screening only) ^d	x											x		x	x
CCI															
Supine vital signs ^f	x														
Supine 12-lead ECG ^g	x														
Dispensation of study intervention															
On-site study intervention administration with meal ^h															
Standardized meals/snacks												x	x		
Blood sampling for:															
CCI															
Hematology, chemistry (inc. eGFR)	x														
CCI															
Lipids, TSH, free T4, calcitonin, amylase, lipase, TBA, PT/INR/aPTT	x														

PFIZER CONFIDENTIAL

Protocol Activity (See Appendix 10 for abbreviations)	Screen	Study Day (all activities at 0H [prior to AM meals/dosing] unless otherwise specified)										Follow Up		ET	
		V2		V3	V4	V5	V6	V7	V8	V9	V10		V11	V12 ^a	
Visit		V1	0	1	2	3	4	5	6	7	8	9-10	12-13		
Weeks Relative to Dosing on Day 1															

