Days Relative to Dosing on Day 1 ^b	-28 to -3	Day -2 to Day 1	2	8	15	22	29	36	43	50	Day 55 to Day 56	57	58	63 - 70 84 - 91	
FSH (females only)	x														
HIV, HepBsAg, HepBcAb, HCVAb, syphilis	x														
Pregnancy test (females only)	x		x	x	x	x	x	x	x	x		x	x		
PF-06882961 PK ⁱ		x		x		x		x	x	x		x	x		
CCI															c
Urine Sampling for:															
Urine drug test	x														
Urinalysis (and microscopy, as appropriate)	x			x		x		x	x	x		x	x		
On-site urine pregnancy test (females only) ^j			x	x	x	x	x	x	x	x		x	x		

- a. Contact may occur via telephone and must occur 28 to 35 days from administration of the final dose of study intervention.
- b. Allowable time window for V3-V10 is ± 1 .
- c. Review glucometer and glucose log only.
- d. Physical examination may be performed at non-specified visits if there are findings during the previous exam or new/open AEs, if appropriate and at investigator discretion.
- C** f. Includes blood pressure and pulse rate; vital signs at Follow up, and early termination visit (if appropriate) are single; Triplicate vital signs should be conducted at Screening, prior to AM dose at 0H and at approximately 4H after AM dose on Days 8, 15, 22, 29, 36, 43, and 50. On Day 57, triplicate vital signs collected at 0H only. When a meal or snack is scheduled at the same time as vital signs, vital signs must be obtained prior to the meal/snack (See [Appendix 9](#)).
- g. 12-lead ECG at Screening, Days 15 and 43, Follow up, and early termination visit (if appropriate) are single; Triplicate ECGs should be conducted prior to AM dose at 0H and at approximately 4H after AM dose on Day 29. On Day 57, triplicate ECGs collected at 0H only. When a meal or snack is scheduled at the same time as an ECG, the ECG must be performed prior to the meal/snack (See [Appendix 9](#)).
- h. During inpatient stays, both AM and PM dosing will occur on the study site, except discharge day (Day 2). On outpatient visit and discharge day, AM dosing will occur at the study site, if applicable.
- i. PK samples to be collected prior to AM dose and at 4H after AM dose on Days 15, 29, and 43. Day 2 sample to be collected at 24H after AM dose on Day 1. Day 50 sample to be collected at 24H after AM dose on Day 49. Day 57 sample to be collected at 24H and 36H after AM dose on Day 56. Day 58 sample to be collected at 48H after AM dose on Day 56.

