- j. At each V2 through V10, the test result must be reviewed and deemed acceptable (ie, negative), in order to continue participation in the study.

Table 2. Schedule of Activities: Visit 2 (V2) and Visit 10 (V10)

[Procedures at 0H to be completed prior to AM dosing or similar clock time, in the case of Day-1]

Study Day ^a	Day -2 (V2) Day 55 (V10)	Day -1 and Day 1 (V2) Day 56 (V10)												
		0	0.25	0.5	1	1.5	2	3	4	6	8	10	12	14
Hours Relative to Dosing at 0H^b	-													
Admission (after ≥8-H fast) and continued inpatient stay at study site	x	→	→	→	→	→	→	→	→	→	→	→	→	→
Adverse event monitoring	x	→	→	→	→	→	→	→	→	→	→	→	→	→
Review prior and concomitant treatments	x	→	→	→	→	→	→	→	→	→	→	→	→	→
Review contraception use (females only)	x													
Review of eligibility criteria (Day -2 only)	x													
Counseling on diet/exercise guidelines (Day -2 only)	x													
Dispense glucometer and supplies, dosing diary, glucose log & provide training (Day -2 only)	x													
Review dosing diary, glucometer & glucose log (Day 55 only)	x													
Glucometer measurement (8 hours fasting, via glucometer)	x ^c	x ^c												
TriPLICATE, supine vital sign assessment ^d		x			x		x		x		x		x	
TriPLICATE, supine 12-lead ECG		x			x		x		x		x		x	
CCI [REDACTED]		x												
Randomization in trial (Day 1 only)		x												
Study intervention administration with meal (starting on Day 1 and thereafter)	x	x ^f									x			
Mixed Meal Tolerance Test (Days -1 and 56 only)		x												
Standardized meal/snack ^g	x	x ^h							x		x		x	
Blood sampling for:														
Hematology, chemistry (inc. eGFR) (Day -1 and 56 only)		x ⁱ												
CCI [REDACTED] Lipids, TSH, free T4, calcitonin, amylase, lipase, TBA, PT/INR/aPTT (Day -1 and 56 only)		x ⁱ												
CCI [REDACTED]		x	x	x	x	x	x	x	x	x	x	x	x	
Pregnancy test (females only)	x													
PF-06882961 PK (Days 1, 55 and 56 only)	x	x ⁱ			x		x		x	x	x	x	x	
CCI [REDACTED]		x	x	x	x	x	x	x	x	x	x	x	x	
Urine sampling for:														
Urinalysis (and microscopy, as appropriate) (Day -1 only)		x												
On-site urine pregnancy test (females only) ^k	x													

a. Day relative to start of study treatment (Day 1).

b. On Day -1, nominal time to match approximate clock time of collection planned on Day 1 to permit time matched comparison.

PFIZER CONFIDENTIAL

- c. Glucometer measures taken before breakfast on all days while inpatient.
- d. Includes blood pressure and pulse rate at all time points.

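### The schedule gives a near-Tmax ECG on 3 of the 5 days with a 4-hour PK sample, and none is scheduled at 120 mg BID until Day 56

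*Protocol*

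**What the plan says.** Protocol Section 4.2 explains why ECG and blood pressure are measured near the peak. Beyond the predose measurements, "triplicate ECG and BP measurements will also be collected at the approximate time to reach" Cmax, "on PK sampling days as specified in the" SOA, so that any drug effect can be better quantified. The sentence before it allows exceptions to triplicate collection where the SOA notes them.

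The SOA (Section 1.3, Table 1 and footnotes) then sets the following:

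- Footnote i: "PK samples to be collected prior to AM dose and at 4H after AM dose on Days 15, 29, and 43".
- Footnote g, on replication: "12-lead ECG at Screening, Days 15 and 43, Follow up, and early termination visit (if appropriate) are single".
- Footnote g, on timing: "Triplicate ECGs should be conducted prior to AM dose at 0H and at approximately 4H after AM dose on Day 29", and "On Day 57, triplicate ECGs collected at 0H only".
- Table 1 header, default timing: "all activities at 0H [prior to AM meals/dosing] unless otherwise specified".
- Footnote f: triplicate vital signs at 0H and about 4H on Days 8, 15, 22, 29, 36, 43 and 50.

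Table 2 gives serial triplicate ECGs on Days -1, 1 and 56, including 4H, and PK at 4H on Days 1 and 56. It shows no ECG on Day 55, and footnote g lists none for Day 50.

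**The concern.** Section 4.2 treats ECG and blood pressure alike. On Days 15 and 43 the SOA delivers the blood pressure half (triplicate at 4H) but not the ECG half. The participant is on site at 4H on both days, with blood drawn for PK and vital signs taken, and no tracing is scheduled.

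Day 43 matters more than Day 15. ECG parameters are part of the primary endpoint (Section 3), and Section 4.3.1 gives the reason for the 120 mg arm: to examine safety up to the highest dose that might enter Phase 3. In that arm 120 mg BID starts on Day 43, after that day's predose ECG. Near-peak ECG information at 120 mg therefore rests on Day 56 alone. A participant who stops between Day 43 and Day 55 contributes none. The early termination ECG is single and is not tied to a time after dosing. If poor tolerability is a reason for stopping, that loss may not be random.

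There is also an effect on analysis. SAP Section 6.1.2 plots QTcF double differences against concentration wherever both are recorded. The 4H concentrations on Days 15 and 43 have no scheduled QTcF partner.

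**Working it through.** No sample size or error rate is involved. The check sets the schedule against the titration table.

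**Inputs.** Weekly doses from Protocol Table 3; ECG times from footnote g and Table 2; PK times from footnote i and Table 2; Tmax of 3 to 6 hours after the morning dose from Section 2.2.2.2. Study week = floor((day − 1)/7) + 1, so Day 15 is in Week 3, Day 29 in Week 5, Day 43 in Week 7 and Day 56 in Week 8.

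**The 120 mg arm, on the five days with a 4H PK sample**

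| Day | Dose (BID) before the 0H tracing | Morning dose that day | ECG scheduled | ECG within 3–6 h |
|---|---|---|---|---|
| 1 | none | 10 mg | triplicate, 0, 1, 2, 4, 8, 12 h | yes (4 h) |
| 15 | 20 mg | 40 mg | single, 0 h by default | no |
| 29 | 60 mg | 80 mg | triplicate, 0 and 4 h | yes (4 h) |
| 43 | 100 mg | 120 mg | single, 0 h by default | no |
| 56 | 120 mg | 120 mg | triplicate, 0, 1, 2, 4, 8, 12 h | yes (4 h) |

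**Coverage.** A near-Tmax ECG is scheduled on 3 of 5 days. With about 9 participants in each of 3 active arms (27):

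- scheduled pairs: 27 × 3 = 81
- possible pairs: 27 × 5 = 135
- proportion: 81/135 = 60%

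**Gap at 120 mg.** 56 − 43 = 13 days, or 13 × 2 = 26 doses before the Day 56 morning dose. The visit window is ±1 day. If the dose step follows the visit, the interval runs from 55 − 44 = 11 to 57 − 42 = 15 days.

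**Other arms.** The 40 mg arm reaches target in Week 3 and the 80 mg arm in Week 5. Both have near-peak triplicate ECGs at target dose on Days 29 and 56, so the top-dose gap belongs to the 120 mg arm alone.

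**Usability of a 4H tracing.** The SAP baseline is the time-matched Day -1 triplicate mean, and Day -1 includes 4H. A 4H ECG on Day 15 or 43 would therefore have its baseline already, and the double difference in SAP Section 3.1.2 could be formed without new definitions.

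**The case against.** The strongest reply is that there is no conflict. Section 4.2 defers to the SOA twice, once for triplicate collection and once for near-Tmax timing, and Section 8.2.4 also sends the reader to the SOA for ECG times. Footnote g is specific, and a site would know what to do. This stands. A reader might infer that the protocol gives two incompatible instructions; the text does not support that.

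A reader might also count only the outpatient days and report 1 day in 3, or 27 pairs of 81. Section 4.2 speaks of PK sampling days, and Days 1 and 56 are the full profile days, so the fair count is 3 in 5. Likewise, the 27 days from Day 29 to Day 56 overstate the top-dose gap, because they include the weeks at 80 mg and 100 mg, and 80 mg has a near-peak ECG on Day 29.

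Nor is the heart unobserved near peak in this period. Triplicate pulse rate and blood pressure at 4H on Days 36, 43 and 50 span both top dose steps. Section 2.2.2.1 reports heart rate increases, and no clear adverse trend in ECG intervals, in an earlier study dosed up to 120 mg BID. Unplanned visits are allowed. The analyses are descriptive, and Day 56 supplies serial ECGs with matched PK in every arm, so no planned analysis fails.

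What remains is that vital signs do not measure QTcF, PR or QRS. The permission to depart from triplicates concerns replication and does not explain why the near-peak tracing is absent. The gap at 120 mg is the same whichever text governs.

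**Conclusion.** The point holds as a cheap improvement. The SOA meets the Section 4.2 aim for ECGs on 3 of 5 days (about 81 of 135 pairs). In one arm of about 9 participants it schedules no ECG at the top dose for 13 days after that dose starts.

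This rests on three assumptions:

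- The Day 15 and Day 43 ECGs are predose. Footnote g states no time for them, and the marks in the Table 1 ECG row were not readable in the text available. The header default, and the explicit 4H entry for Day 29 only, both support this reading.
- Week 1 starts on Day 1 and doses step up on the nominal visit days. If steps follow the calendar and the Day 43 visit falls a day late, its predose tracing would follow the first 120 mg doses, but it would still be a trough value.
- The count covers scheduled ECGs in participants who complete; unscheduled and early termination tracings are extra.

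It would be wrong to conclude that ECG safety at 120 mg goes unassessed, or that the planned ECG summaries cannot be produced.

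**What to change.** Reconcile Section 4.2 with footnote g by one of these routes:

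1. **Retime.** State in footnote g that the single ECGs on Days 15 and 43 are taken at about 4H, just before the 4H PK sample and lunch. This needs no extra tracing or visit. It costs the predose ECG on those days and its pairing with the predose PK sample, so the total number of pairs is unchanged but two become near-peak. The tracing stays single, so Section 4.2 should say so.
2. **Add.** Keep the predose tracing and add a 4H ECG on both days while the participant is on site. This costs a few minutes per visit. Only an added triplicate meets Section 4.2 in full.

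Either route raises near-Tmax pairs from about 81 to 135 and, in the 120 mg arm, gives a tracing 4 hours after the first 120 mg dose. If neither is adopted, narrow Section 4.2 to name Days 1, 29 and 56 as the days with near-Tmax ECGs. The SAP needs no change to its baseline or double-difference definitions.
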